5.1.2 General study level definitions

5.1.2.1 Analysis time points

5.1.2.1.1 Relative day

The relative day of an event will be derived with the date of first dose of study medication as reference.

Relative day for an event or measurement occurring before the date of first dose in the study will be calculated as follows:

$$\text{Relative Day} = \text{Event Date} - \text{Date of First Dose}$$

The relative day for an event or measurement occurring on the date of first dose is day 1. The relative day for an event or measurement occurring on or after the first dose and before the date of the last dose will be calculated as follows:

$$\text{Relative Day} = (\text{Event Date} - \text{Date of first Dose}) + 1$$

For events or measurements occurring after the date of last dose of study medication (within the SFU period), relative day will be prefixed with “+” in the data listings and will be calculated as follows:

$$\text{Relative Day} = +(\text{Event Date} - \text{Date of Last Dose})$$

There is no relative Day 0. Relative day will not be calculated for partial dates. In such cases, relative day should be presented as “--” in the relevant data listing.

5.1.2.1.2 End date of the treatment period

The end date of the treatment period will be either the date of the month 18 EOT visit (visit 15) for participants who complete the treatment period, or the date of the EOT visit for participants who discontinue the study during the treatment period (same procedures as visit 15 for completers). If a study participant does not have an EOT visit then the date of the last scheduled or unscheduled visit during the treatment period or the date of last known dose of study medication (whichever is later) will define the end date of the treatment period.

5.1.2.1.3 Study periods

The total duration of the study per participant is approximately 21 months. The end of the study is defined as the date of the last visit of the last participant in the study. The following study periods are defined for this study:

Screening period:

The screening period will last 3 to 6 weeks and includes 2 visits to the investigational site (Visit 1 and Visit 2). At Visit 1 the participants provide informed consent and undergo screening to assess eligibility for the study. At Visit 2, additional assessments to verify eligibility, including DaT-SPECT imaging, will be performed. Participants consenting to its use will also receive a wearable sensor (the wearable sensor) for 2-3 weeks for familiarization at home. This is to address potential technical issues and to collect stable Baseline data for the sensor. The sensor will be finally returned by the participant to the clinic on Visit 15 (M18 visit, or Early Termination Visit in case of early study termination).

Treatment period:

The treatment period will last for 18 months and may include both investigational site visits and telemedicine video calls with the site (see schedule of activities in protocol section 1.3 for more detail). During video calls a research nurse will support the participant at the participant's home. The treatment period ends with Visit 15 (EOT).

During the treatment period, participants will receive either UCB0599 (360mg/day), UCB0599 (180mg/day) or placebo with a 1:1:1 randomization ratio.

Safety follow up period:

The safety follow up will last for approximately 30 days and includes 1 visit (the Safety Follow-Up (SFU) visit). The SFU visit may be a telehealth video call with the investigator, supported by the research nurse. For those participants who do not roll over to the extension study (PD0055), the study ends with the SFU Visit approximately 30 days after the last dose. Participants who enter the extension study will not enter the SFU period and their final visit will be visit 15.

Early termination:

In case of early termination of a participant's treatment, the participant will be asked to attend the End of Treatment (EOT) and the SFU visit (30 days after the last dose) and will not be eligible for the dose-blinded extension study (PD0055).

5.1.2.1.4 Mapping of assessments performed after early termination

Study participants who discontinue the study for any reason will be asked to attend the End of Treatment (EOT) and the SFU Visit (30 days after the last dose) and will not be eligible for the extension study (PD0055). Participants will be encouraged to attend these two visits as soon as possible after last dose of study drug.

The following rules will apply regarding the inclusion of data obtained at the EOT visit for participants who discontinue:

- If the early EOT visit occurs at the same time as the next scheduled visit, the results will be included with all other participants' results from that visit in summary tables
- If the above is not true, the results will be mapped to the nearest scheduled visit following the last scheduled visit where assessments were performed (use the earliest visit if equidistant)
- If results are then mapped to a visit where the assessment is not performed, these results will be listed only and not included in any summaries
- Mapped results will be included in any statistical analyses (where applicable)

These rules apply to all data, with the exception of DaT-SPECT scan results. As scans are only planned three times throughout the study, the above mapping rules will not be used as we would often map to visits where a scan is not scheduled. For rules for mapping EOT visit DaT-SPECT scans for participants who discontinue early, and also for out of window DaT-SPECT scans, see [Section 5.3.2.3](#).

The results from these early end of treatment visits will be displayed as the mapped visit and flagged in the data listings. Early SFU visit results will not be mapped to another visit but will be flagged in data listings. Results from early SFU visits will be listed but will not be included in summary tables and figures, unless explicitly stated otherwise (for example, impact of COVID-19 summaries).

For all statistical analyses, data for participants who terminate early will be handled using the pre-specified ICE strategies (see [Section 1.2](#) for further details). If the data is to be included in the analysis, the mapping rules above will be used.

5.1.2.1.5 Definition of baseline values

In general, Baseline values will be determined from the latest non-missing value collected prior to the first dose of study medication, unless otherwise stated for a specific analysis in later sections.

If day 1 pre-dose data is collected per the schedule of activities then this will be used as the Baseline value, if not the latest screening data will be used. All day 1 assessments will be assumed to have been taken pre-dose. If day 1 pre-dose data is supposed to be collected but is not for any reason, this should be investigated before automatically using the latest screening value.

5.1.2.2 Protocol deviations

Important protocol deviations (IPDs) are deviations from the protocol which could potentially have a meaningful impact on study conduct or on either the primary or key secondary outcome(s) for an individual study participant. The criteria for identifying such protocol deviations will be defined within the IPD specifications document.

Important protocol deviations will be categorized as follows:

- Inclusion/exclusion criteria deviations
- Incorrect treatment or dose administered
- Procedural non-compliance
- Prohibited concomitant medication use
- Withdrawal criteria deviation

All protocol deviations will be reviewed as part of the ongoing data cleaning process and all important deviations will be identified and documented before unblinding. Important protocol deviations will be listed and summarized. Three data evaluation meetings (DEMs) will be held throughout this study, with the final DEM occurring just before database lock. The purpose of these DEM reviews will be to review all protocol deviations and check the quality of the data. The reviews will also help decide how to manage problems in the study participants' data (eg, missing values and withdrawals).

Accepted deviations from scheduled time points will be described in the appropriate documents and included in the eTMF. After the pre-analysis review, resolution of all issues, and documentation of all decisions (including inclusion into each of the analysis sets) at the final DEM, the database will be locked.

Some protocol deviations will be pre-defined as ICEs and the handling of these deviations is discussed in [Section 1.2](#).

5.1.2.3 Treatment assignment and treatment groups

Participants will be randomized in a 1:1:1 ratio to receive either UCB0599 high dose (360mg/day), UCB0599 low dose (180mg/day) or placebo. All listings and summaries will be presented by treatment group unless stated otherwise. [Appendix 4](#) outlines which summaries should present an overall summary as well as data summarized by treatment group.

Table 5–2: Treatment group descriptions

Full Description	Data Display Label
Placebo	Placebo
UCB0599 360mg/day (180mg BID)	Minzasolmin 360mg/day
UCB0599 180mg/day (90mg BID)	Minzasolmin 180mg/day
UCB0599 pooled high dose (360mg/day) and low dose (180mg/day)	Minzasolmin Total

If after unblinding it is determined that participants received treatment other than what they were randomized to, then for baseline characteristics, safety and PK analyses participants will be allocated to the treatment they predominantly received (ASPS, RS, SS and PKS assignment will be based on actual treatment). Treatment assignment for the FAS will be allocated based on randomized treatment and not actual treatment received, all efficacy analyses will be based on the FAS. A sensitivity analysis will be performed for the primary estimand where actual treatment assignment is used.

5.1.2.4 Center pooling strategy

The data from different centers will be pooled for all analyses. Data for some endpoints will be summarized by region/country as described in [Section 5.1.2.6](#).

5.1.2.5 Coding dictionaries

Adverse events and medical history will be coded using the latest available version of the Medical Dictionary for Regulatory Activities (MedDRA®). Medications will be coded according to the latest available version of the World Health Organization Drug Dictionary (WHO Drug-Global B3 format). Medical procedures will not be coded.

5.1.2.6 Multicenter studies

Since treatment assignment will not necessarily be balanced across countries or sites, no statistical analyses will be carried out to investigate center effects. However, for the primary endpoint and for some pre-specified secondary endpoints, summary statistics will be produced by region (Europe and North America).

For each region summary statistics for both observed results and changes from Baseline by visit (Baseline, months 12 and 18 where applicable) and treatment group will be produced for the following endpoints:

- MDS-UPDRS Part I-III sum score;
- MDS-UPDRS Part III;
- MDS-UPDRS Part III ePD subscore (UCB in-house)
- MDS-UPDRS Part III – First 3-point Increase;
- MDS-UPDRS Part II;
- MDS-UPDRS Part II – First 3-point Increase;
- MDS-UPDRS Part I;
- MoCA;
- DaT-SPECT mean striatum SBR;
- Levodopa cumulative daily dose (summary of changes from Baseline not needed for this endpoint).

These summaries will also present the number of participants included in each treatment group by region.

In addition, for each country and region, the following counts will be summarized by visit and treatment group, overall and by gender:

- The number of participants on ST.

In addition, in response to the COVID-19 pandemic, the number of participants who contracted COVID-19 during the study (further details given in [Section 5.2](#)) will be summarized by treatment group and visit, overall and by country/region.

5.2 Participant dispositions

The number of study participants who started the study, completed the study, prematurely discontinued, and who enter the extension study will be presented by treatment group and overall. The reasons for discontinuation will also be summarized. This summary of disposition and discontinuation will be based on the RS. A study participant who completed the study is defined as a study participant who has a completed status in the study termination CRF. Since the primary estimand analysis in this study will be done using the first 12 months of data for each participant, the number of completers and the number of premature discontinuations will be summarized separately up to this time (in the same summary table). Participants who discontinue early are considered to have completed month 12 if their study termination date falls in or after the month 12 visit window.

The number and percentage of study participants who discontinue due to AEs will be summarized by treatment group, based on the RS. This summary will be used for European Union Drug Regulating Authorities Clinical Trials (EudraCT) reporting. This table will also present (separately) discontinuations due to AEs prior to the month 12 visit.

The number and percentage of study participants included in each of the analysis sets will be summarized by treatment group. Numbers will be presented for all analysis sets (including the ASPS) but percentages will be calculated based on the RS for the purpose of this summary. Additionally, a listing based on the SS will be produced for participants excluded from the FAS, including the reason for exclusion.

Screen failure reasons will be summarized for the ASPS. A separate summary will also be produced summarizing the reasons for ineligibility for those who screen fail due to being ineligible. A listing of study participants who did not meet study eligibility criteria will also be presented for this analysis set.

In addition, the following listings will be presented:

- Disposition of study participants (ASPS)
- Study discontinuation (RS)
- Visit dates (RS)
- Study participant analysis sets (ASPS)
- Rescreened Participants (ASPS)

The listing of disposition of study participants will include the date of informed consent, date of first and last dose of IMP, date of premature termination and primary reason (if applicable), date of final contact and whether the participant entered the extension study.

The listing of study discontinuation will include the reason for discontinuation and the number of days on IMP.

The number of days on IMP will be calculated as follows:

$$\begin{aligned} \text{Number of Days on IMP} \\ = (\text{Date of Last Dose Received} - \text{Date of First Dose Received}) + 1 \end{aligned}$$

Additionally, a summary of the impact of COVID-19 (for any reason) will be produced by country and treatment group for the RS. This information will also be listed for the ASPS. Potential impacts that will be included in these summaries are missed visits or doses, visits performed out of window or through a different modality, and temporary/permanent study or drug discontinuation. Relationship to COVID-19 will also be included in these outputs, detailing whether the impact is due to confirmed infection, suspected infection or general COVID-19 related circumstances.

Two additional outputs will be produced for use in the Plain Language Summary (and are not required for the CSR):

- Summary table of disposition of participants screened (showing the dates of the first participant in and out at each site, as well as analysis set counts by site)
- Listing of actual treatment assignment by site and participant

5.3 Efficacy estimands and endpoints

All efficacy data will be listed based on the FAS. All summaries and analyses for efficacy estimands and endpoints will be presented for the FAS.

Statistical outputs

For all statistical models fitted to the efficacy data, diagnostic plots will be included in the statistical output documents. The statistical outputs for all models will include the following treatment group comparisons:

- a. UCB0599 high dose (360mg/day) versus placebo,
- b. UCB0599 low dose (180mg/day) versus placebo,

For some key analyses (defined elsewhere), the model output summary table will also present the percentage change in mean slope or in mean difference at Month 12/18 for each dose-level against placebo (ie, the difference in slope/mean divided by the placebo slope/mean multiplied by 100).

For some key analyses (defined elsewhere), the mean slope or the mean difference at Month 12/18 for each dose-level against placebo will be depicted in forest plots with either corresponding 95% CIs or 80% CIs, the latter to match the type I error used in the trial sample size estimation.

MDS-UPDRS score derivation

For all MDS-UPDRS analyses, MDS-UPDRS Part I-III and subscales (Part I, Part II, Part III) sum scores will only be calculated if responses are available for all questionnaire items. If one item response is missing, for example in Part I, Part II and Part III sum scores can still be calculated but Part I and Part I-III sum scores will not be calculable. However, missing responses to individual items within the questionnaire are not expected.

To calculate the sum scores, the response scores to the following items will be summed:

- Part I: items 1.1 to 1.13, sum score ranges from 0 to 52;
- Part II: items 2.1 to 2.13, sum score ranges from 0 to 52;
- Part III: items 3.1 to 3.18 (for Part III some items will be tested on both side of the body and on the upper as well as the lower limb – all responses will be summed to get the Part III total score, 33 items in total), sum score ranges from 0 to 132;
- Part I-III: items 1.1 to 1.13, 2.1 to 2.13 and 3.1 to 3.18, sum score ranges from 0 to 236.

When MDS-UPDRS is collected at home rather than in clinic not all MDS-UPDRS data will be collected (rigidity assessments will be missing) and the Part III and Part I-III sum scores cannot/will not be calculated. Part I and Part II sum scores can still be calculated and used in any analyses, assuming all item responses are collected.

Symptomatic Treatment Status and other ICES

For all summary tables and listings where ST status is used or presented, the assumption is made that once a participant starts ST, they remain on ST for all study visits after their initiation date.

For summary tables that are being presented for participants who are not yet on ST, this means not yet on ST by a particular visit. This means that the number of participants contributing to the summary will differ by visit in the table, as more participants may have initiated ST by the following visit.

For plots that are displayed by ST initiation timing, the following categories will be defined for participants who started ST:

- By month 2 (inclusive);
- between month 2 and 4 (inclusive);
- between month 4 and 6 (inclusive);
- between month 6 and 8 (inclusive);
- between month 8 and 10 (inclusive);
- between month 10 and 12 (inclusive);
- between month 12 and 18 (inclusive);
- not started by 18 months/EOT.

To support the efficacy analyses presented in this section, a (cumulative) summary table presenting the number and percentage of participants with each ICE (see [Section 1.2](#) for a full list of the ICEs defined in this study) will be produced by visit.

Modelling considerations

Baseline covariates

For any analyses adjusting for continuous covariates, these covariates will be mean centered to aid interpretability (the intercept term can be interpreted as the expected value of the response when the dependent variables are set to their means). When mean centering covariates, the calculated mean will be based on the data used for that estimand analysis. All efficacy models will include age at baseline as a covariate. Since this study was randomized stratifying for gender, gender should be included as a covariate in all efficacy models unless explicitly stated otherwise.

As stated in [Section 4](#), for all analyses, a participant should only be included in the model if they have a baseline score for the endpoint being analyzed.

Estimation considerations and Convergence issues

If convergence problems are encountered, model (any) will be run without adjusting for age at baseline. If convergence issues persist, check that all variance components are positive or not too close to zero. If a variance component is negative or close to zero, then attempt to simplify the structure of the relevant variance-covariance matrix. If convergence issues are solved by using a simplified variance-covariance structure, age at baseline may be added back into the model if appropriate.

For Mixed Effects Models, the following steps will be implemented:

- Linear random coefficients model with Time as continuous: the most common issue will be for the estimate of covariance between the subject and the subject-time random coefficients. In this case, set the corresponding covariance in the G variance covariance matrix (RANDOM statement) to 0 to obtain a separate variance component for each random effect (TYPE = VC) and re-run the model:

$$G = \begin{pmatrix} \sigma_{\text{participant}} & 0 \\ 0 & \sigma_{\text{participant-time}} \end{pmatrix}$$

- ANCOVA/Repeated measures model with Time as categorical: set the structure of the variance-covariance matrix to a compound symmetry structure (instead of ARH1 in the case of MDS-UPDRS or unstructured in the case of DaT-SPECT).

For details, refer to Brown and Prescott, 2014.

5.3.1 Primary estimand analysis: MDS-UPDRS Part I-III sum score slope of progression over 12 months, in the absence of ST initiation

For the primary estimand analysis, only data from the first 12 months of the study will be considered. The primary estimand is for the primary efficacy objective, which is to demonstrate the superiority of UCB0599 over placebo with regards to clinical symptoms of disease progression over 12 months.

5.3.1.1 Definition of endpoint

The primary endpoint for each participant is slope of progression in MDS-UPDRS Part I-III sum score measured bi-monthly over 12 months or up to the time of ST initiation, including Baseline score and scores at 2, 4, 6, 8, 10 and 12 months.

Descriptive statistics

Although the primary estimand is based only on data up to month 12, descriptive statistics discussed here for MDS-UPDRS Part I-III sum score will be presented for the entire 18-month period.

Summary tables presenting the observed mean and mean change from Baseline in MDS-UPDRS Part I-III sum score by treatment group and visit will be produced. This summary will be produced overall and by ST status, where ST status is defined as having or not having initiated ST.

Plots of individual MDS-UPDRS Part I-III sum score over time by treatment group and gender will be presented, color-coded to clearly indicate when a participant is and is not on ST. These plots will be grouped by ST initiation timing category.

In addition to these individual plots, plots of observed mean MDS-UPDRS Part I-III sum score and mean change from baseline will be produced by treatment group and ST initiation timing category, overall and by gender. These plots will include error bars (+/- SD) and all treatment groups will be overlaid on the same plot.

All planned summary tables and plots of MDS-UPDRS Part I-III sum score will also be produced for the sum scores of each individual subscale (Part I, II and III).

5.3.1.2 Main analytical approach

Details on the ICE handling for this estimand can be found in [Section 1.2](#). All data recorded after a participant initiates ST will be censored.

A Linear Mixed Effects Model (LMEM) here, a random coefficients model for longitudinal data will be applied to the data up to the time of ST initiation. MDS-UPDRS Part I-III sum score will be the dependent variable, Baseline MDS-UPDRS data will be part of the dependent variable rather than a covariate in the model. Time since baseline in months, as a continuous variable and the treatment by time interaction (fixed slope) will be fitted as fixed effects (Twisk et al, 2018), gender and age at baseline will be included in the model as covariates. To adjust for the correlation between repeated observations from each participant, a participant-specific random intercept and a participant-specific random slope (ie, participant by time interaction or random time effect) will be fitted as random effects (Twisk, 2013). The random effects will induce the correlation structure in the marginal model (ie, the model not conditional on random effects following integrating them out).

A fixed effect for treatment will not be included in this model. This implicitly assumes that the Baseline values for all three groups are equal and reflected in the intercept of the model. The treatment effects can therefore be directly obtained from the treatment by time interactions (slope or rate of progression).

The population-level summary for this estimand will be the difference in population mean slope of progression in MDS-UPDRS Part I-III sum score over 12 months in the absence of ST initiation between:

- UCB0599 high dose (360mg/day) and placebo
- UCB0599 low dose (180mg/day) and placebo.

The estimates of these will come from the treatment by time interaction from the above model. These estimates are to be interpreted as the unit increase in MDS-UPDRS Part I-III sum score per month, after adjusting for gender and age at baseline. A summary table presenting these estimates with the corresponding 95% confidence intervals will be produced. A repeat of this summary table will also be produced presenting the model estimates to 1 decimal place only, for use in the study Plain Language Summary (this table is not required for the CSR).

A plot displaying the adjusted mean slope and 95% confidence interval for each treatment group from this model will be produced.

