- Unblinded pharmacometrics staff and statistical programmers, independent from the study team, who have access to the 12-month data for the preparation of the exposure-response analysis

To balance prognostic factors across treatment groups, randomization of study participants will be stratified using permutation blocks by gender.

In the Parkinson Progression Markers Initiative (PPMI) database, variability in MDS-UPRDS was observed to differ between male and female PD patients. Men and women also behave differently with respect to start of ST. Therefore, the study will balance treatment groups according to gender.

In the three-arm study, only participants who are recruited after the introduction of the randomization schedule which include the low-dose arm will have a chance of being assigned to low-dose UCB0599, causing a small time bias. This time bias will be considered to have no impact on how the participants respond to their assigned treatment, ie, the data collected from participants assigned to the placebo and high-dose arms prior to the introduction of the full randomization schedule will be assumed comparable to the data collected from participants assigned to the placebo and high-dose arms after the introduction of the full randomization schedule.

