ASYN=alpha-synuclein; CGII=Clinical Global Impression of Improvement; CGIS=Clinical Global Impression of Severity; CSF=cerebrospinal fluid; DaT-SPECT=Dopamine Transporter Imaging with Single Photon Emission Computerized Tomography; ePD=early-stage PD; EQ-5D-5L=EuroQol-5-dimension-5-level; HADS=Hospital Anxiety and Depression Scale; MDS-NMS=Movement Disorder Society-Non-motor Scale; MDS-UPDRS=Movement Disorder Society-Unified Parkinson's Disease Rating Scale; MoCA=Montreal Cognitive Assessment; PD=Parkinson's Disease; PGIC=Patient Global Impression of Change; PGIS=Patient Global Impression of Severity; PRO=Patient-Reported Outcome; RMET=restricted (t-year) mean event time; SBR=specific binding ratio; SE-ADL=Schwab and England Activities of Daily Living; ST=symptomatic treatment

Note: "In the absence of concomitant ST intake" means that all data recorded after a participant initiates ST will be censored. "Regardless of concomitant ST intake" means that participant data will be included in the analyses even after they have initiated ST. If a participant does not comply with the 12-hour ST washout prior to any visit, the data from that particular visit will be censored.

Efficacy data analysis at 12 and 18 months will take place once all participants have completed their 18-month Visit. All efficacy analyses will be carried out for the FAS and adjusted for the randomization stratification factor (ie, gender) and age at Baseline.

Treatment will be coded as a categorical variable with 3 levels (placebo, UCB0599 high dose, and UCB0599 low dose) with placebo as the reference category.

For change from Baseline analysis, treatment will be fitted as a fixed (main) effect. For longitudinal analyses of covariance and repeated measures modeling in which Baseline value is used as outcome, a treatment by time interaction will be included in this model as implicitly, the Baseline values for all groups are assumed to be equal and are reflected in the intercept of the models (Twisk, 2013).

Where applicable, explanatory continuous covariates will be mean-centered so that the intercept term can be interpreted as the expected value of the response when the dependent variables are set to their means.

Where reported alongside estimates and corresponding confidence intervals (CIs), p-values will always be presented as continuous values.

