### Estimates

Estimates for the treatment effects of interest (see above) over 12 months (MDS-UPDRS units increase per month) adjusted for gender and age at Baseline, with corresponding 95% CIs.

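### The slope models adjust only the level for gender and age, so the primary slope difference called adjusted for them is in practice unadjusted

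*SAP*

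**What the plan says.** SAP 5.3.1.2 gives the fixed part of the primary model. Time in months and "the treatment by time interaction (fixed slope) will be fitted as fixed effects"; then "gender and age at baseline will be included in the model as covariates". There is no treatment main effect, and neither document specifies a gender-by-time or age-by-time term. The treatment effect is read straight from treatment-by-time, and the SAP describes the estimate as "the unit increase in MDS-UPDRS Part I-III sum score per month, after adjusting for gender and age at baseline".

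The protocol uses similar language. Section 9.3 has all efficacy analyses "adjusted for the randomization stratification factor (ie, gender) and age at Baseline", and the Estimates paragraph of 9.3.1.1.1 has the slope effects "adjusted for gender and age at Baseline, with corresponding 95% CIs". The general rule in SAP 5.3 is that "gender should be included as a covariate in all efficacy models unless explicitly stated otherwise"; it does not mention interaction with time.

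The same model serves the de-mediated slope analysis (SAP 5.3.1.4.3), the Part III slope (5.3.2.1.2) and the supplementary de-mediated slopes (5.3.2.1.4), and is restated in Appendix 6.5.6. Section 5.3.2.1.2 describes its estimate as adjusted for gender alone, although it refers back to the same model.

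Protocol 6.3 gives the reason for stratifying by gender: MDS-UPDRS variability differs between the sexes in the PPMI data, and "Men and women also behave differently with respect to start of ST". It does not say that the rate of progression differs.

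**The concern.** A main effect of gender or age moves a participant's whole line up or down. It says nothing about how steep the line is. The estimand is a difference in steepness, so covariates entered this way explain none of the between-person variation in slope, and they do not correct a slope difference that arises because one arm happens to be older. Gender is balanced by stratification. Age is not a stratifier, so only the model can deal with a chance age imbalance.

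Two things are at stake. Any precision that the stratifier and age could offer for the primary comparison is left unused. And the report would describe the slope difference as adjusted for two covariates that hardly touch it.

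**Working it through.** **1. Reproduce the planned sample size.** Inputs from SAP 3.1, Table 3-1 and 3.2: random-intercept variance 154.0, random-slope variance 0.43, residual variance 31.1, placebo slope 0.90 per month, N1·Var(T) = 85.57, Z = 2.56, effect 0.3 × 0.90 = 0.27 per month, equal allocation. With both variance terms placed under the factor (1 + 1/λ) = 2, the SAP formula reduces to

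n = 2 × (0.43 + 31.1/85.57) × Z² / 0.27²

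The per-person slope variance is 0.43 + 0.363 = 0.793, so n = 2 × 0.793 × 6.554 / 0.0729 = 142.7, against 143 stated. (With the brackets read literally as printed, the formula gives 104; the grouped form is the one that matches.) At 143 per arm the standard error is √(2 × 0.793/143) = 0.105, and power at one-sided 10% is Φ(0.27/0.1053 − 1.2816) = 90.0%. SAP 3.1 says that the PPMI model behind these inputs had no baseline covariates, so the 143 does not rest on the adjustment.

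**2. What covariate-by-time terms could gain.** Let R be the share of the 0.43 that gender and age explain. The documents give no value, so R is an assumption, and zero is included. The per-person variance becomes 0.43(1 − R) + 0.363.

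| R | Slope variance | Fall | n per arm for 90% power | Power at 143 |
|---|---|---|---|---|
| 0% | 0.793 | 0% | 142.7 | 90.0% |
| 5% | 0.772 | 2.7% | 138.8 | 90.6% |
| 10% | 0.750 | 5.4% | 134.9 | 91.2% |
| 20% | 0.707 | 10.8% | 127.2 | 92.4% |

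**3. Do the planned main effects reach the slope at all?** They are not wholly inert, because baseline is part of the response and is constrained equal across arms. This was checked by simulation: 1000 trials per setting, two arms of 143, seven bimonthly visits, monotone loss to 35% at Month 12, gender-stratified allocation, Table 3-1 variances treated as known, and intercept–slope correlation of 0 or 0.43. Assumptions not in the documents: 62% male, age SD 8.5 years, level effects of 2 points for gender and 0.25 points per year of age, and the slope effects below. Simulated standard errors should be compared with one another, not with the 0.105 above, because the simulated loss pattern does not reproduce 85.57 exactly.

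- Adding the planned main effects to a model without covariates moves the treatment-by-time estimate by an SD of 0.003 to 0.004 per month, about 1 to 1.5% of 0.27.
- Adding covariate-by-time terms moves it by an SD of 0.007 if slopes do not depend on gender or age. The SD is 0.013–0.015, 0.023–0.025 and 0.035–0.036 for assumed gender slope differences of 0.2, 0.3 and 0.45 per month with age effects of 0.01, 0.02 and 0.03 per month per year.
- In those three settings the mean standard error goes from about 0.111 under the planned model to about 0.110, 0.107–0.108 and 0.102–0.103. With no covariate effect on slope it is 0.111 either way.
- The planned model averages −0.267 to −0.274 for a true −0.27, so it shows no bias.

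**4. Chance age imbalance.** At an assumed age effect of 0.03 per month per year, each year of difference in mean age between arms shifts the planned estimate by about 0.03, or 0.03/0.27 = 11% of the target effect; the fuller model removes this shift. With the assumed age SD of 8.5, the SD of the between-arm difference in mean age is 8.5 × √(2/143) = 1.0 year, so an imbalance of that size is ordinary.

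**The case against.** The strongest reply is that no rule is broken. SAP 5.3 asks for gender and age as covariates, and 5.3.1.2 includes them. Randomisation is stratified by gender, the random slope absorbs between-person differences in progression, and the planned estimate is unbiased. The size of any gain is assumed throughout; at a 5% share it is 0.6 of a percentage point of power, and at zero it is nothing. SAP section 2 also calls the study exploratory and warns against over-reading p-values. All of this stands, and it limits the point to a small improvement and a correction of wording.

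A reader might go further and infer that censoring at ST start biases the comparison, because the sexes differ in starting ST and the mean slope ignores gender. The documents do not support that. The likelihood model conditions on each participant's observed trajectory. Distorting the contrast would need slopes that depend on gender together with ST censoring whose gender pattern differs by arm, and neither document gives such slopes or rates. The supplementary de-mediated analyses also carry sex and age group in their imputation, propensity and lag-effect models (Appendix 6.5.4 and 6.5.5).

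A reader might also extend the point to the repeated-measures models. There the target is a visit mean, which main effects of gender, age and baseline do adjust, so no defect is shown. Covariate-by-visit terms would add 8 + 8 = 16 parameters with nine post-baseline visits.

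**Conclusion.** The point holds for the slope models. The slope difference described as adjusted for gender and age is practically unadjusted for both: the planned main effects move it by about 1 to 1.5% of the target effect. The consequences are unused precision, no protection against chance age imbalance, and a misleading label. The estimate is not biased, and neither the 143 per arm nor its 90% power is in question. The gain from correcting it runs from nothing to about 2.4 percentage points of power as the explained share goes from 0 to 20%. That range is an assumption, since the documents report no effect of gender or age on slope. The change is worth making because it costs almost nothing even if the true share is zero.

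**What to change.** Before database lock, amend SAP 5.3.1.2, and with it 5.3.1.4.3, 5.3.2.1.2, the slope analysis in 5.3.2.1.4 and Appendix 6.5.6:

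- Add gender-by-time and age-by-time fixed effects to the slope models only, and keep the main effects.
- Mean-centre both over the participants in the analysis. SAP 5.3 now centres continuous covariates only. With gender uncentred, the time coefficient becomes the placebo slope of the reference gender, and the percentage change defined in 5.3 divides by the placebo slope. The treatment difference itself does not depend on the centring.
- The convergence rule in 5.3 removes age first. State that age-by-time leaves and returns with age, and that gender-by-time stays.
- Bring the description in 5.3.2.1.2, which names gender only, into line with the common model.

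If the terms are not added, stop describing the slope difference as adjusted for gender and age. The cost is two fixed-effect parameters per slope model and SAP wording, with no new data. Leave the repeated-measures models as they are.
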